15.2.4 Follow-up Visit V04 (day 10)

The final visit will be performed on study day 10 (-1; +2 days).

The final visit examination is performed in order to verify if the patient is cured. A patient will be considered cured, if no living head lice could be detected. If living lice present on day 10, the life stages of the lice will be documented. If any other pediculocidal agents employed during the observation period, the patient will be considered a treatment failure.

The following examinations will be performed within the final visit:

- Hair scalp assessment for living lice (all stages) by study staff
- Assessments of skin and eyes irritation, global tolerability, local tolerability
- Questioning on well-being
- Questioning on patient's combing
- Registration and documentation of any adverse events and/or changes regarding concomitant diseases, concomitant medication, withdrawal criteria

In case that the examination (diagnostic combing) will show active head lice infestation (living nymph or imago), the patient will be considered treatment failure or re-infestation and will be referred to a specialist for further treatment.

Subjects exhibiting either subjective or objective abnormalities when the trial has been completed will be followed up. Any AE which remains unresolved after completion of the trial requires detailed evaluation and follow-up until the AE has been resolved or a reasonable

explanation for its persistence is found. If the subject refuses to follow the instructions of the study staff, the latter is released from responsibility.

At the final visit each trial subject participating in this study will be advised not to participate in any clinical drug studies for a minimum period of two months following this study.

15.3 Restrictions

- No parallel use of any other anti-head lice therapy
- Female patients are to be informed that they have to apply adequate contraceptive methods (e.g. uterine tube sterilisation, sexual abstinence or vasectomised partner or combination of anti-conceptive medication and condom, spermicidal products, diaphragm, temperature method).

15.3.1 Miscellaneous

A pregnancy test in urine will be performed for all female patients with childbearing potential at visit 1 (Screening Visit).

After signing the informed consent patients will receive their subject number, after performing checks for exclusion/inclusion the subjects will receive their random number.

The activities and measurements will be done in the course of the trial as given in the trial flow chart in chapter 3.

For all assessments with exemption of local tolerability, global tolerability, skin irritation and eyes irritation assessment, a deviation up to ± 20 min from scheduled time will be accepted.

For children who are unable for self-assessment and documentation, their guardians will take over these tasks.

15.4 Administration of investigational products

Firstly, a sufficient quantity of the investigational products will be evenly applied by an unblinded investigator or by specially instructed staff onto dry hair.

The amount applied depends on the length of the patient's hair. For the test product the hair should be covered completely with the product.

For GOLDGEIST[®] FORTE, the following recommendations were given (see table below). Infants will be treated with a maximum amount of 25 mL. However, no more of the investigational product will be used, as necessary to properly cover the hair and scalp.

Category	Hair length	Volume of GOLDGEIST [®] FORTE applied
1	short hair	about 25 mL
2	hair reaching the patient's shoulders	about 35 – 40 mL
3	hair from patient's shoulders until mid-back	about 75 mL

The test product shampoo will be evenly dispensed (massage) in the hair over its full length, (with special diligence on the base of the hair near the scalp). After 10 minutes without

covering the hair a sufficient amount of water will be added to the hair to work up foam. A deviation up to plus 2 minutes due to organisational reasons, particularly to deal with children's ability to follow strict procedures will be accepted. Afterwards the foam will be washed out without shampoo and the hair will be rinsed thoroughly.

The reference product GOLDGEIST[®] FORTE will be evenly dispensed (massage) in the hair over its full length, (with special diligence on the base of the hair near the scalp). After at least 30 up to 45 minutes without covering the hair, the product will be washed out with warm water. A deviation up to plus 5 minutes will be accepted.

No shampoo must be used for rinsing both investigational products.

Afterwards the hair will be carefully towel-dried. Completely drying the hair using a hair dryer will be performed by the patients themselves or their guardians.

A description of the administration will be given in a specific instruction sheet.

15.4.1 Subject and treatment compliance

The subject's compliance will be monitored during in-house visits by study staff. Any subject found not following directions and restrictions will be withdrawn from the study. Details of the reason for removal of subjects will be reported.

During and after administration of the particular investigational products the patients will strictly follow the instruction of the investigator or study team.

Each investigational product will be administered of one of the study staff. The assessor (blinded study personnel) will check the head of each patient after administration.

15.5 Assessments

Assessments for skin irritation and eyes irritation directly prior to administration (baseline as well as assessments on day 7) will be performed within 1 hour before administration.

Assessments for local tolerability, global tolerability, skin irritation and eyes irritation after administration will be performed directly after start of the treatment plus 5 minutes as well as after the end of administration (the contact time is over and the investigational product is rinsed) within 15 minutes.

For all other assessments a deviation up to ± 20 min from scheduled time will be accepted.

15.5.1 Global tolerability assessment

Global tolerability will be assessed by blinded study staff and by the patient or his/her guardian at day 10. The study staff will perform the rating in each case prior to the assessment by the patient to avoid bias. Afterwards, the patient will self-assess the global tolerability.

The global tolerability will be rated on a 4-category scale with:

Score 1 = very good

Score 2 = good

Score 3 = moderate

Score 4 = poor

15.5.2 Local tolerability assessment

Subjective symptoms (burning, paraesthesia, pruritus) after administration of the investigational products will be rated by the patients on a 4-category scale at day 0 (0h, 1h p.a.) and day 7 (0h, 1h p.a.) directly after study drug application, day 1 (24h), and day 10 p.a.:

Score 1 = no

Score 2 = mild

Score 3 = moderate

Score 4 = severe

It will be investigated, whether the treatments have any influence on the above mentioned subjective symptoms.

15.5.3 Skin irritation assessment

Skin irritation (secondary infection, erythema, excoriation) will be assessed by blinded and trained study staff within 1 hours before first treatment (baseline), as well as directly after study drug application and after the end of treatment on study day 0, day 1, day 7 (pre-treatment, 0h and 1h p.a.) and on day 10.

For the assessment of skin irritation the following 4-category scale as mentioned above will be used.

Score 1 = no

Score 2 = mild

Score 3 = moderate

Score 4 = severe

It will be investigated, whether the investigational products may cause symptoms of skin irritation.

15.5.4 Eyes irritation assessment

To investigate a potential irritation of the eyes due to the treatment, the trained and blinded study staff will be assessed the severity of redness on both eyes (left, right) within 1 hours before first treatment (baseline), as well as directly after study drug application and after the end of treatment on study day 0, day 1, day 7 (pre-treatment, 0h and 1h p.a.) and on day 10.

For the assessment of eyes the following 4-category scale as mentioned above will be used.

Score 1 = no

Score 2 = mild

Score 3 = moderate

Score 4 = severe

It will be investigated, whether the investigational products may irritate the eyes.

15.5.5 Assessment of esthetical properties

The esthetical properties of the investigational products will be evaluated to determine the satisfaction by the patients with the products after application using a questionnaire about hair and scalp feeling, greasiness, hair look, shininess and volume. The questioning will be performed on day 0 and day 7 after treatment and drying the hair.

1. Your hair does not feels to dry after treatment.

Score 1 = strongly agree Score 2 = agree Score 3 = disagree Score 4 = strongly disagree

2. Your scalp feels pleasant after treatment.

Score 1 = strongly agree Score 2 = agree Score 3 = disagree Score 4 = strongly disagree

- 3. The greasiness of your hair after treatment is normal.
- Score 1 = strongly agree
- Score 2 = agree

Score 3 = disagree

- Score 4 = strongly disagree
- 4. Your hair looks good after the treatment.
- Score 1 = strongly agree
- Score 2 = agree
- Score 3 = disagree
- Score 4 = strongly disagree
- 5. The shininess of your hair after treatment is fine.

Score 1 = strongly agree

Score 2 = agree

Score 3 = disagree

Score 4 = strongly disagree

- 6. The volume of your hair after treatment is fine.
- Score 1 = strongly agree
- Score 2 = agree
- Score 3 = disagree
- Score 4 = strongly disagree

15.5.6 Assessment of the hair and scalp (diagnostic combing)

An assessment of the hair and scalp will be performed to determine the number of live lice in the hair with a special lice comb (dry combing). This assessment will be done only for diagnostic reasons. The patients will be instructed to use a lice comb as recommended in the leaflets of the investigational products between the study days. The lice comb will be provided by Oystershell.

For this assessment the hair will be divided into 3 sections: left, middle, and right side of the head. Each section will be combed with a lice comb and the number of live lice encountered per section is recorded. The hair will be assessed for lice on day 0 to determine if the subject complies with the inclusion criterion: \geq 5 live lice. This procedure will be repeated on day 1, day 7 (pre-treatment) and day 10.

The life stage of lice found during assessments on day 1, day 7 and day 10 must be recorded as this is necessary for determination of re-infestation (see 15.6.1). In case that the examination on day 1, day 7 or day 10 will show active head lice infestation (living nymph or imago), the lice caught by the comb will be discarded. The patients with active head lice infestation on day 10 will be considered a treatment failure and will be referred to a specialist for further treatment.

15.6 Efficacy measurements

The endpoints for efficacy assessment will be based on the cure rate on day 10 p.a. The cure rate is defined as proportion of patients without any live lice, corrected for the rate of re-infestations.

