10.1 Primary objective

The primary objective is to show that the cure rate after local application of test product **sector** is better than a predefined limit. It has to be shown, that the test product **sector** achieves a cure rate superior to 70% (cure rate at the end of day 10, corrected for re-infestation).

Hereby, the following primary endpoint is investigated:

 Cure rate at the end of day 10 (corrected for re-infestation) for the test product for all baseline infestations

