15.6.1 Re-infestation

A re-infestation [22] is defined as:

- a) no adult lice or third stage nymphs present following the first treatment AND
- b) no more than two adult lice or third stage nymphs found by combing on day 10.

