16.3 Analysis of primary objective

The cure rate p is defined as proportion of patients who will be found to be cured at evaluation follow-up-visit V04 among all patients received any treatment at visit V01.

The aim of the study is to show superiority for the cure rate of investigated treatment p_T versus a predefined limit of 70%. This limit refers to cure rates found for several formulations which are accepted for the intended use.

The following null hypothesis will be tested:

 $H_{0,prim}$: $p_T = 70\%$

If $p_T > 70\%$ and the null hypothesis is rejected by a two sided, one sample χ^2 -test at 0.05 level, superiority will be concluded.

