16.5 Determination of sample size

The design of the trial including the number of subjects is adapted from a previous trial performed with Silcap shampoo [24] and based on statistical calculation.

According to [21], a 90% cure rate can be expected for the study medication. In general, a cure rate of 70% can be assumed to a minimal accepted cure rate. The primary objective refers to superiority of cure rate vs. this limit. A sample size of 42 is required for a one group χ^2 -test comparing cure rate of 90% with a fixed limit of 70% (two sided test; alpha-level of 0,05; power=90%; software nQuery advisor 7.0; power=80%: sample size=34).

For the reference group, the identical sample size is used. Assuming 10% drop outs and a 5% rate for re-infestation, the sample size has to be multiplied by 1.1×1.05 leading to approximately 50 cases (exactly: 49 cases which have been rounded up to 50 cases).

The sample size is also applicable to show secondary objectives 3 and 4, if following cure rates are assumed:

Superiority: 60% vs 90% (90% power), 65% vs. 90% (80% power).

Non inferiority (margin: -7,5%): 70% vs. 90% (90% power).

¹ For practical considerations: Note that the half width of one sided 0.025 one sided CI and two sided 0.05 two sided CI are equal.

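### The primary cure rate is to be corrected for re-infestation, but the protocol never says how, and sections 15.5.6, 15.2.4, 16.3 and 16.5 do not treat re-infested patients alike

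*Protocol*

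**What the plan says.** The primary endpoint in protocol section 10.1 is "Cure rate at the end of day 10 (corrected for re-infestation) for the test product for all baseline infestations". Section 15.6 repeats the idea: "The cure rate is defined as proportion of patients without any live lice, corrected for the rate of" re-infestations. Section 15.6.1 defines who is re-infested: (a) no adults or third-stage nymphs after the first treatment, and (b) "no more than two adult lice or third stage nymphs found by combing on day 10". It does not say how such a patient counts.

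Four other sections bear on that:

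- **15.5.6:** "The patients with active head lice infestation on day 10 will be considered a treatment failure". There is no exception, although the same paragraph has life stages recorded so that re-infestation can be determined.
- **15.2.4:** with living lice at V04, "the patient will be considered treatment failure or re-infestation". Section 11 also names the two outcomes separately.
- **16.3**, which defines p for the test: patients cured at V04 "among all patients received any treatment at visit V01". It mentions no correction and no exclusion.
- **16.5:** "Assuming 10% drop outs and a 5% rate for re-infestation, the sample size has to be multiplied by" 1.1 × 1.05.

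**The concern.** If 15.5.6 and 16.3 are followed literally, the correction named in 10.1 and 15.6 does nothing: a re-infested patient has live lice, is a failure and stays in the denominator. If 10.1 and 15.6 are followed, something must be done with these patients, and three operations are open: count them as not cured, remove them, or count them as cured. The choice affects the primary test against 70%. It also affects the same test in the reference arm and the superiority and non-inferiority comparisons in 16.4, which use the same cure rates.

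**Working it through.** **Inputs.** From 16.3 and 16.5: limit 70%, two-sided one-sample chi-square test at 0.05, planned rate 90%, 10% drop-out, 5% re-infestation, 50 per arm. The patient counts in step 2 are assumptions.

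**1. The plan's own figure.** n = [1.960·√(0.7·0.3) + z·√(0.9·0.1)]² / 0.2².
- 90% power (z = 1.282): 41.13, so 42, as stated.
- 80% power (z = 0.842): 33.10, so 34, as stated.
- Inflation: 42 × 1.1 × 1.05 = 48.51, so 49, rounded to 50, as stated.

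The arithmetic is sound. The factor 1.05 makes sense only if re-infested patients no longer contribute to the test. Counting them as failures or as cured loses nobody and would not call for a larger n.

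**2. One data set, three readings.** z = (x/n − 0.7)/√(0.21/n). Assume 50 treated and 40 lice-free.

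| Reading | 3 re-infested | p | 2 re-infested | p |
|---|---|---|---|---|
| Not cured | 40/50 = 80.0% | 0.123 | 40/50 = 80.0% | 0.123 |
| Removed | 40/47 = 85.1% | 0.024 | 40/48 = 83.3% | 0.044 |
| Counted as cured | 43/50 = 86.0% | 0.014 | 42/50 = 84.0% | 0.031 |

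The planned 5% of 50 is 2.5 patients, so 2 and 3 bracket it.

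**3. How often the verdict changes.** Take n = 50 and 5% re-infestation, and sum the multinomial probabilities of all outcomes in which the three readings do not agree.
- If 90% applies only to patients who are not re-infested, the lice-free, re-infested and failed probabilities are 0.95 × 0.90 = 0.855, 0.05 and 0.095. The readings disagree in about 25% of trials.
- If 90% is the overall lice-free rate, the probabilities are 0.90, 0.05 and 0.05. They disagree in about 6%.

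**4. Power if re-infested patients are failures.** At n = 50 the test rejects from 35 + 1.960·√10.5 = 41.35, so from 42 cured. P(X ≥ 42 | 50, 0.90) = 0.942 and P(X ≥ 42 | 50, 0.855) = 0.704. Under the first assumption in step 3, exact power falls from 94% to 70%.

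**5. The rule in 15.6.1.** Condition (b) sets a maximum of two and no minimum. A patient who is clear after the first treatment and has zero lice on day 10 meets (a) and (b). A denominator that simply subtracts everyone meeting 15.6.1 would drop most cured patients while the numerator keeps them, and the rate could exceed 100%.

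**The case against.** Section 17 leaves analysis details to an SAP to be finalised before database lock, and that SAP could supply the formula. This is fair as far as it goes. However, the protocol itself fixes the failure rule in 15.5.6 and the denominator in 16.3, and these do not give the endpoint named in 10.1. An SAP would have to override one of them.

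Three stronger readings are tempting, and the document does not support them.

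- A reader might infer that the protocol removes re-infested patients. No section says so. Removal is inferred from the factor 1.05; the inference is close, but it is not a stated rule. Likewise, the sentences in 15.2.4 and 11 are mainly about referral and do not define an analysis class.
- A reader might infer that the choice decides the trial in general. It does so only near the threshold. The example sits at 80% lice-free, well below the planned 90%. With 43 lice-free and 2 or 3 re-infested, all three readings reject, because 43/50 alone gives p = 0.014.
- A reader might infer that the formula will be picked after the results are seen in an open trial. Section 14.4 blinds the lice assessor and section 17 requires the SAP before lock, so the protocol does not plan this. Blinding protects the louse count, though, and does not settle the formula.

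It is also fair to say that an all-treated primary rate would be as coherent as one that excludes re-infested patients.

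**Conclusion.** The concern stands as a failure to define the primary endpoint operationally, with sections 15.5.6, 15.2.4, 16.3 and 16.5 not aligned. The primary rate cannot be computed uniquely from the protocol. This should be fixed before any outcome data are analysed.

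The size is conditional. The p-values of 0.12, 0.024 and 0.014 come from assumed counts near the boundary. The share of trials in which the verdict depends on the reading is about 25% or about 6%, according to what the planned 90% means, and 16.5 does not say. The fall in power from 94% to 70% holds only if the 90% excludes re-infested patients. The sample-size arithmetic itself is correct.

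**What to change.** State one formula in 16.3 and align 15.5.6, 15.6 and 15.6.1 with it. To match the sizing in 16.5:

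- **Numerator:** patients with no live lice at V04.
- **Denominator:** all patients treated at V01, minus those who have live lice on day 10 and also meet 15.6.1. Use the same rule in both arms.
- **15.6.1:** add a lower bound to (b), at least one live louse on day 10, and state which visits the wording of (a) covers (day 1, day 7 or both).
- **15.5.6:** except these patients from the failure sentence, for the analysis classification only.
- **Sensitivity analysis:** pre-specify the uncorrected all-treated rate, with re-infested patients as not cured, under the same test. Report whether the conclusion holds under both.
- **16.5:** say whether the 90% already allows for re-infestation.

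If the sponsor prefers the all-treated rate as primary, swap the two analyses and restate the power in 16.5.

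The cost is wording in these sections and one extra table. The downside for the sponsor is that a claim resting only on the correction becomes visible.

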15.6.1 Re-infestation

A re-infestation [22] is defined as:

- a) no adult lice or third stage nymphs present following the first treatment AND
- b) no more than two adult lice or third stage nymphs found by combing on day 10.

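### The re-infestation rule counts only adults and third-stage nymphs, so patients with younger live nymphs on day 10 can be corrected out of the primary cure rate

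*Protocol*

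**What the plan says.** The primary endpoint in Protocol section 10.1 is "Cure rate at the end of day 10 (corrected for re-infestation) for the test product for all baseline infestations". Section 15.6 adds: "The cure rate is defined as proportion of patients without any live lice, corrected for the rate of re-infestations". Section 15.6.1 decides who is re-infested by two joint conditions. Condition (a) concerns the combings once treatment has begun: "no adult lice or third stage nymphs present following the first treatment". Condition (b), which must hold as well, puts a ceiling on the final combing: "no more than two adult lice or third stage nymphs found by combing on day 10".

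Two other sections classify the day-10 finding. Section 15.5.6 defines active infestation as a living nymph or an adult louse and makes every patient with active infestation on day 10 a treatment failure. Section 15.2.4 says that such a patient is either a treatment failure or a re-infestation, and that a patient with no living lice is cured.

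Section 15.5.6 also links the stage records to this rule. Life stage on days 1, 7 and 10 "must be recorded as this is necessary for determination of re-infestation". Section 16.3 takes the cure rate "among all patients received any treatment at visit V01" and does not mention the correction.

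**The concern.** Both conditions in section 15.6.1 limit only adults and third-stage nymphs. First- and second-stage nymphs play no part, although they are live lice and their stage is recorded. A patient whose only day-10 finding is young nymphs, in any number, therefore meets the literal definition. So does a patient with one or two older lice among many young ones.

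This matters because young nymphs are a plausible sign of eggs that survived treatment. Section 8.1 claims that the test product kills eggs as well as lice, and inclusion criterion 3 requires at least five apparently live eggs. A product that cleared adults but spared eggs could have failures of this kind relabelled as re-infestation. The primary test against 70% would then see a higher cure rate than was achieved.

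**Working it through.** **1. The plan's own figure.** Section 16.5 gives 42 per arm for 90% against 70% (two-sided 0.05, 90% power). The normal approximation gives n = [1.96·√(0.7·0.3) + 1.2816·√(0.9·0.1)]² / 0.20² = 41.13, so 42. Then 42 × 1.1 × 1.05 = 48.51, so 49, rounded to 50. The figure reproduces, and this point does not change it.

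**2. The definition applied case by case.** Condition (a) is taken as met: no adult or third-stage nymph after the first treatment.

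| Day-10 combing | Meets 15.6.1 as written | Meets the rule proposed under the fix |
|---|---|---|
| 1–2 adults or third-stage nymphs, no younger nymph | yes | yes |
| 1 young nymph only | yes | no (failure) |
| 20 young nymphs only | yes | no (failure) |
| 2 older lice and 20 young nymphs | yes | no (failure) |
| 3 older lice | no | no (failure) |

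Condition (a) ignores young nymphs too, so a patient with young nymphs at every combing would still qualify as written.

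**3. Whether another section repairs this.** If section 15.5.6 prevailed, every patient with a live louse on day 10 would be a failure. Nobody could be corrected, and the correction in sections 10.1 and 15.6 would be empty. Section 15.2.4 keeps re-infestation as a possible class. The sections conflict, and none says which governs.

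**4. How relabelling enters the test.** The protocol does not say whether a re-infested patient counts as cured or leaves the denominator. Section 16.3 keeps all treated patients, whereas the 5% inflation in section 16.5 suggests exclusion. Both routes are shown.

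With n = 50, the one-sample χ²-test claims superiority from 42 cured: (0.84 − 0.70)/√(0.21/50) = 2.16, above 1.96; 41 cured gives 1.85. Let f be the share of all patients who are failures with young nymphs but are relabelled. With true cure rate p:

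- counted as cured: P(X ≥ 42) with X ~ Bin(50, p + f);
- dropped: the number dropped is Bin(50, f), the apparent rate among the rest is p/(1 − f), and the critical value is recalculated for each remaining n.

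Exact chance of claiming superiority:

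| f (assumed) | p = 70%, dropped | p = 70%, counted as cured | p = 65%, dropped | p = 65%, counted as cured |
|---|---|---|---|---|
| 0 | 0.0183 | 0.0183 | 0.0025 | 0.0025 |
| 2% | 0.0342 | 0.0365 | 0.0053 | 0.0058 |
| 5% | 0.0665 | 0.0916 | 0.0118 | 0.0183 |
| 10% | 0.1865 | 0.3073 | 0.0429 | 0.0916 |

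The nominal level in this direction is 0.025. The 5% row equals the re-infestation allowance in section 16.5. The calculation assumes no genuine re-infestation and no dropout.

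**5. A single data set, for scale (invented counts).** Take 40 of 50 lice-free: 80.0%, z = 0.10/√(0.21/50) = 1.54, p = 0.123. Suppose three of the ten failures have only young nymphs. Dropped: 40/47 = 85.1%, p = 0.024. Counted as cured: 43/50 = 86.0%, p = 0.014.

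**The case against.** The strongest reply is that section 15.6.1 should not be read alone. Section 15.5.6 makes failure the default for any living nymph. Condition (b) can be read as listing the only lice that may count as re-infestation, so that young nymphs alone stay failures. The definition is also taken from a cited source that is not at hand. This shows that a sensible reading exists, but the text does not impose it. Zero is no more than two, and the section 15.5.6 default, applied as written, would abolish the correction altogether.

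Several stronger readings are tempting, and the documents do not support them.

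- A reader might infer that lice-free patients are classed as re-infested because condition (b) has no lower limit. Sections 15.2.4 and 15.6 class them as cured, and section 15.2.4 raises re-infestation only where living lice are found. The missing limit is a matter of wording.
- A reader might infer that the visits for condition (a) are left open. Section 15.5.6 ties the day 1 and day 7 records to this decision, so naming them is again a clarification.
- A reader might call the bias unbounded. The nymph count per head has no limit, but the cure rate can rise by no more than the share of day-10 failures.
- A reader might infer a bias between arms. That needs a difference in egg kill between the products, for which the documents give no data.
- The origin of young nymphs in surviving eggs is an inference; the documents give no hatching times.

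**Conclusion.** The point holds for young nymphs. As written, section 15.6.1 lets patients with live first- or second-stage nymphs on day 10 count as re-infested, and no other section settles the matter. If 5% of patients were relabelled at a true cure rate of 70%, the chance of a false superiority claim would be about 0.07 to 0.09 instead of 0.018; at 2%, about 0.03 to 0.04; at 10%, 0.19 to 0.31. At a true rate of 65% it stays below 0.025 for shares up to 5% and reaches 0.04 to 0.09 at 10%.

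The true share cannot be derived from the documents, so these figures show sensitivity and do not estimate the bias. The conclusion about the text needs no assumption. The conclusion that true failures are removed needs young nymphs to reflect incomplete treatment. Because the rule feeds the primary test and is cheap to repair, it should be corrected before outcomes are classified.

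**What to change.** Rewrite section 15.6.1 so that re-infestation applies only to patients with live lice on day 10 and requires all of:

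- (a) no adult or third-stage nymph at the day 1 combing or at the day 7 pre-treatment combing;
- (b) one or two adults or third-stage nymphs on day 10;
- (c) no first- or second-stage nymph on day 10.

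Every other patient with a live louse on day 10 is an endpoint failure. Reconcile the endpoint classification in sections 15.2.4, 15.5.6, 15.6 and 16.3, and state how the correction enters the numerator and the denominator. Add a sensitivity analysis that counts every patient with live lice on day 10 as a failure.

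The cost is a short text amendment and one extra analysis. No new data are needed, since section 15.5.6 already requires it: "The life stage of lice found during assessments on day 1, day 7 and day 10 must be recorded". The drawback is that fewer patients will qualify as re-infested, so the corrected cure rate may be slightly lower.
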